4.5 Patient Registration

Participants may be registered from 8:00 am to 4:00 pm EST excluding holidays by emailing the study monitor at: [contact]. Eligible participants will be entered on study centrally once the following items have been received by email:

- Completed registration form
- Consent and HIPAA signature pages
- Eligibility checklist

Following registration, participants must begin protocol treatment within 7 days of registration. Issues that would cause treatment delays must be discussed with the Principal Investigator. If a registered participant does not receive protocol therapy following registration, the participant will be recorded as withdrawn from study. The Study Monitor must be notified as soon as possible if a participant does not begin protocol treatment as scheduled. For additional registration questions, please email **[contact]**

The study monitor or their designee will notify the site by email once registration is confirmed and the sequence number has been assigned. Participants must be registered and have received a sequence number prior to the initiation of treatment.

Exceptions to the current registration policies will not be permitted.

5.0 Treatment Modifications

5.1 Dose Reductions

In the event of alopecia, HFS, or stomatis, only capecitabine dose will be reduced according to the following table.

Hand and Foot	Management/Next Dose for Capecitabine		
Syndrome/Stomatitis/Alopecia			
Grade 1	No change in dose		
Grade 2	Hold until \leq Grade 1. Resume at same dose level.		
Grade 3	Hold until < Grade 1. Resume at one dose level lower, if		
Glade 5	indicated. (Per Section 5.2 Dose Levels)		
Grade 4	Off protocol therapy		

In the event of other toxicities that are specifically attributable to capecitabine (such as hand-foot syndrome, diarrhea), the dose of capecitabine will be delayed or reduced first. If toxicity progresses or does not improve within 72 hours after capecitabine delay or reduction, quinacrine will also be delayed/ dose-reduced. Dosing delays/modifications will be done according to the following schema:

Diarrhoa	Management/Next Dose for	Management/Next Dose for	
Diamiea	quinacrine	capecitabine	
Grade 1	No change in dose	No change in dose	
	Hold until \leq Grade 1. Resume at	Hold until \leq Grade 1. Resume at	
	same dose level.	same dose level. If it reoccurs, hold	
Grade 2		until < Grade 1 and resume at one	
		dose level lower. (Per Section 5.2	
		Dose Levels)	
	Hold until < Grade 1. Resume at	Hold* until < Grade 1. Resume at	
Grade 3	one dose level lower, if indicated.	one dose level lower, if	
Clauc 5		indicated.** (Per Section 5.2 Dose	
		Levels)	
Grade 4	Off protocol therapy	Off protocol therapy	
Recommended management: Loperamide antidiarrheal therapy			
Adjunct anti-diarrheal therapy is permitted and should be recorded when used.			

All other toxicities	Management/Next Dose for	Management/Next Dose for	
All other toxicities	quinacrine	capecitabine	
Grade 1	No change in dose	No change in dose	
Crada 2	Hold until \leq Grade 1. Resume at	Hold until \leq Grade 1. Resume at	
Grade 2	same dose level.	same dose level.	
	Hold until < Grade 1. Resume at	Hold until < Grade 1. Resume at	
Grade 3	one dose level lower, if indicated.	one dose level lower, if indicated.	
		(Per Section 5.2 Dose Levels)	
Grade 4	Off protocol therapy	Off protocol therapy	

Recommended management for nausea: antiemetics

If treatment needs to be held for more than 3 weeks due to severe treatment related toxicities that cannot be resolved despite maximum supportive care, the patient will be taken off protocol therapy.

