*NA indicates that the action taken is the same regardless of whether there were patients previously treated at a higher dose

The MTD will be used at recommended phase 2 dose (RP2D) unless there are any safety concerns. Patients who needed a dose reduction after being treated with RP2D in phase I will receive the reduced dose in phase II.

For the purposes of quinacrine dose escalation, the dose-limiting toxicities (DLT) that will be taken into account include toxicity grade >2 hematological, GI/diarrhea, skin, LFT abnormality or otherwise unexpected grade 3 toxicity or higher, associated with the combination therapy. Quinacrine dose modifications will not be made in the event of toxicities that are primarily attributed to capecitabine; namely, > grade 2 alopecia and hand and foot syndrome (HFS). Patients experiencing DLT will be permitted to continue their treatment after a single step dose reduction.

Intra-patient dose escalation will occur only for patients experiencing Common Toxicity Criteria < grade 2 toxicity on a previous course. The intra-patient dose escalation for a patient in lower level dose cohort will be on hold until the highest dose cohort patient completes first cycle of therapy. For purposes of toxicity assessment, patient response to the initial dose received will be considered. Total time in therapy, however, will be adjudged to include the whole duration the patient received treatment, regardless of the doses received.

General concomitant medications, dose adjustment, drug warnings and supportive care guidelines, duration of therapy, duration of follow up, and criteria for removal from treatment, as described throughout the protocol will be applied to both Phase I and II.

The endpoint of the Phase I portion of this study will occur when the safety and tolerability of the quinacrine-capecitabine combination is evaluated. Based on our preclinical data and the history of use of both capecitabine and quinacrine, we expect that the following regimen will be safely tolerated by the majority of patients.

	Premedications;				Cycle
Agent	Precautions	Dose	Route	Schedule	Length
Quinacrine	After a meal with a	200 mg tablets	Orally:	Daily on	
	glass of water	Orally twice a	at least 8 hours	Days 1-21	
		day	between each		
			dose		
Capecitabine*	Within 30 minutes	1000 mg/m ²	Orally:	Daily on	21 days
	after a meal with	Orally twice a	at least 8 hours	Days 1-14	(3 weeks)
	water	day	between each		
			dose		

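### Section 5.1 gives incompatible quinacrine instructions for hand-foot syndrome and leaves those for grade 2–3 diarrhea ambiguous

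*Combined protocol and SAP*

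**What the plan says.** Three places govern what happens to quinacrine in these two toxicities.

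- **Section 5.1, opening line and first table.** "In the event of alopecia, HFS, or stomatis, only capecitabine dose will be reduced according to the following table". The table covers hand-foot syndrome (HFS), stomatitis and alopecia, and has no quinacrine column.
- **Section 5.1, next paragraph.** Its scope is set by the words "In the event of other toxicities that are specifically attributable to capecitabine (such as hand-foot syndrome, diarrhea". For events within that scope it fixes an order between the two drugs: "the dose of capecitabine will be delayed or reduced first". Quinacrine enters only at a second step: "If toxicity progresses or does not improve within 72 hours after capecitabine delay or reduction, quinacrine will also be delayed/ dose-reduced". The paragraph ends: "Dosing delays/modifications will be done according to the following schema". The diarrhea table follows. Its quinacrine column holds the drug at grade 2 and resumes it at the same level. At grade 3 it reads "Hold until < Grade 1. Resume at" one level lower, if indicated. The capecitabine column holds that drug at the same grades. A table for all other toxicities comes after it and also holds both drugs at grades 2 and 3.
- **Section 3.1.** "Quinacrine dose modifications will not be made in the event of toxicities that are primarily attributed to capecitabine". The sentence then names alopecia and HFS above grade 2. It stands in a paragraph about quinacrine dose escalation.

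Section 3.1 also states that the dose-adjustment guidance serves both phases.

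**The concern.** Quinacrine is the agent being escalated in Phase I and tested in combination in Phase II, so the rule for interrupting or reducing it should be the same for every patient with the same event. In these two toxicities the rule depends on which line of Section 5.1 the treating clinician follows. Both are common with capecitabine by the protocol's own account: Section 7.2 gives diarrhea in 50% and HFS in 35% to 45%. At stake are consistent handling of patients and a clear meaning for the quinacrine dose actually delivered.

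**Working it through.** The plan states no figure on this point, so the check is a comparison of texts, followed by the little arithmetic the documents allow.

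**Step 1: HFS.**

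| Source | Quinacrine instruction for HFS |
|---|---|
| 5.1 opening line and table | None; capecitabine alone is changed |
| 3.1 | Not modified (HFS above grade 2) |
| 5.1 second paragraph | Delayed or reduced if HFS worsens or has not improved 72 hours after the capecitabine change |

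At grade 1 the first table changes nothing, so the 72-hour trigger does not arise. At grade 4 the patient leaves protocol therapy. The conflict therefore lies at grades 2 and 3, in events that worsen or are unimproved at 72 hours. For such an event, one instruction leaves quinacrine alone and the other changes it. They cannot both be followed.

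**Step 2: diarrhea.**

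| Grade | 5.1 text (event specifically attributable to capecitabine) | 5.1 diarrhea table |
|---|---|---|
| 1 | – | No change, both drugs |
| 2 | Capecitabine first; quinacrine only on worsening or no improvement at 72 hours | Both held; quinacrine resumed at the same level |
| 3 | As for grade 2 | Both held; quinacrine resumed one level lower, if indicated |
| 4 | – | Both off protocol therapy |

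The table carries no capecitabine-first step and no 72-hour condition, yet the text presents it as the schema to be applied. The difference is confined to grades 2 and 3.

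**Step 3: size for one patient with grade 2–3 diarrhea.**

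- Timing: holding quinacrine at once or continuing it for up to 72 hours differs by 3 of the 21 dosing days in a cycle. 3 / 21 = 14.3% of planned doses, which is 3 doses on a once-daily schedule or 6 on a twice-daily schedule.
- Level: if grade 3 diarrhea improves within 72 hours, the text leaves quinacrine unchanged. The table holds it and resumes it one level lower if indicated. Section 5.2 describes a level as a 50% reduction, where a lower level exists.

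**Step 4: number of patients.** Section 7.2 gives frequencies without grade. Applied to the 29 Phase II patients:

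- diarrhea: 29 × 0.50 = 14.5
- HFS: 29 × 0.35 = 10.2 to 29 × 0.45 = 13.1

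These are expected counts of patients with the event at any grade. The affected subset is grade 2–3 for diarrhea, and grade 2–3 that worsens or is unimproved at 72 hours for HFS. The documents give neither share, so the number affected cannot be derived.

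**The case against.** The strongest reply concerns diarrhea. The capecitabine-first text is limited to events specifically attributable to capecitabine. Section 7.3 lists diarrhea for quinacrine as well, so a diarrhea table needs a quinacrine column. Text and table can then be read together: the text sets the order and the trigger, and the table sets the size of the change by grade. That is a sensible reading, and it is why a reader should not infer a flat contradiction on diarrhea. But the protocol does not state it, and it gives no rule for attributing diarrhea to one drug when both can cause it. What stands is an ambiguity.

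Two further points on the text have some weight. The grade 3 capecitabine cell of the diarrhea table carries asterisks whose footnotes are not in the text available here and may have been lost in conversion. They sit only in the capecitabine column, so they would not obviously qualify the quinacrine instruction, but their content is unknown. On HFS, the paragraph begins with other toxicities immediately after the HFS table, so the repeated mention may be a drafting slip in one parenthesis. That may explain the contradiction; it does not remove it.

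On consequences, a reader might infer that the MTD, the RP2D or the observed response rate is distorted. The documents do not show this. DLTs are counted by grade, and a hold made after a grade 3 event cannot undo it. Continuing or stopping quinacrine at grade 2 might influence whether an event reaches grade 3, but that is conjecture without a figure. The Simon two-stage numbers and the toxicity stopping boundaries do not change. Nor are patients left without any rule: for grade 2–3 events of either kind, every reading acts on capecitabine at once, and only the quinacrine action differs.

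Finally, Section 6.2.1 already records the action taken with study drug for each adverse event, and Section 3.2 requires a Phase II medication diary, so the data for describing holds largely exist.

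**Conclusion.** The point holds in two parts of unequal strength. For HFS, Section 5.1 contradicts itself, with 3.1 siding with its opening line above grade 2; this is wrong as written. For grade 2–3 diarrhea, the text and the table are ambiguous in combination. In both cases two clinicians could treat quinacrine differently for the same event and each cite the protocol.

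Per event, the diarrhea ambiguity amounts to up to 3 of 21 days of quinacrine and, at grade 3, possibly one dose level. The any-grade counts of about 14–15 and 10–13 of 29 might be taken as the number of patients affected. They are only loose ceilings, and they assume that the capecitabine frequencies in Section 7.2 carry over to this population. Because these are operative dosing instructions and the repair is cheap, the wording should be corrected, but the point does not call the design or the sample size into question.

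**What to change.** Reconcile the text of 5.1, the tables of 5.1 and the sentence in 3.1 so that each toxicity and grade has one instruction for quinacrine and one for capecitabine. In particular:

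- state once whether HFS ever leads to a quinacrine change, and make every mention agree;
- state whether the 72-hour condition applies to the quinacrine column of the diarrhea table, and how attribution to capecitabine is to be judged if the rule depends on it;
- confirm that the asterisked notes in the diarrhea table are present in the controlled version.

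Which rule applies is for the sponsor's clinical team to decide.

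Optionally, add to Section 11.5 a descriptive summary of delivered quinacrine dose intensity, with holds and reductions by reason, drawn from the action-taken data already collected; none is planned there now.

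The cost is amendment wording. Sample size, endpoints and stopping boundaries are untouched.

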5.2 Dose Levels for Phase II

Dose reductions will be as follows:

Dose Level	Quinacrine	Capecitabine
-2	50% reduction	500 mg/m2, schedule
-1	50% reduction	750 mg/m2, schedule
0	RP2D	1000 mg/m2, schedule

The number of dose de-escalations will depend upon the RP2D. For example if RP2D is 400mg/day of quinacrine and $1000mg/m^2$ of capecitabine 2 dose reductions are possible but if RP2D is 200mg/day of quinacrine and $1000mg/m^2$ of capecitabine of quinacrine only 1 dose reduction is possible or if RP2D is 100mg/day of quinacrine and $1000mg/m^2$ of capecitabine no dose reductions are possible. In this study for Phase 2, dose re-escalations are allowed up to RP2D at the discretion of the treating Physician.

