3.5 Duration of therapy

Treatment continues until at least one of the following criteria applies:

- Disease progression,
- Intercurrent illness that prevents further administration of treatment,
- Unacceptable adverse event(s) (DLT)
- Patient decides to withdraw from the study, or
- General or specific changes in the patient's condition render the patient unacceptable for further treatment in the judgment of the investigator.

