	Chan	ce of e	scalatio	on, MT	D in pl	ace or (de-esca	lation		
pesc:	0.981	0.928	0.847	0.744	0.625	0.496	0.363	0.232	0.109	
pstay:	0.013	0.033	0.043	0.041	0.031	0.018	0.008	0.002	0.000	
pdesc:	0.006	0.039	0.110	0.215	0.344	0.486	0.629	0.766	0.891	
p(T>2)	: 0.100	0.200	0.300	0.400	0.500	0.600	0.700	0.800	0.900	
mtddes	c· 0 99	0 0 93	6 0 82	8 0 67	6 0 50	0 0 32	4 0 1 7	2 0.06	4 0.010)

mtddesc: 0.990 0.936 0.828 0.676 0.500 0.324 0.172 0.064 0.010 Chance of MTD on de-escalation

The primary efficacy endpoint for Phase II is the rate of response by RECIST (CR, PR, SD, PD). The null hypothesis to be tested is that the RP2D observed in Phase I is not efficacious. We will use the standard Simon's two-stage design with 80% power at alpha level 0.05. The response rate is assumed to be 5% for the standard treatment and 20% for quinacrine in combination with capecitabine. The Phase II portion will first enroll 10 patients. The trial will be stopped if no patient responds to treatment. Otherwise, 19 additional patients will be enrolled for a total of 29 patients. The drug will be declared to have sufficient response rate if 4 or more subjects respond to treatment.

The other primary end point for Phase II is time to tumor progression, which will be analyzed by the Kaplan and Meier method.

Toxicity endpoint: If ever 5 of the initial cohort of 10 patients experience DLTs, or if ever 8 of the 29 total evaluable phase II patients do, the trial will be halted for excess toxicity and either dose adjusted or terminated. If the true chance of DLT is 33.3% the trial will be halted in this way with power 80.5%. If the true toxicity is at most 15%, the chance of termination in error is at most 6.3%.

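### Sections 3.1 and 5.2 give different Phase II doses for patients reduced from the RP2D in Phase I, and 3.1 and 3.5 disagree on whether treatment continues after a DLT

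*Combined protocol and SAP*

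**What the plan says.** Four sections bear on the dose after toxicity.

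- **5.2 (Phase II dose levels):** "In this study for Phase 2, dose re-escalations are allowed up to RP2D at the discretion of the treating Physician". No grade, recovery or prior-DLT condition is attached.
- **3.1 (Phase I), carry-over:** "Patients who needed a dose reduction after being treated with RP2D in phase I will receive the reduced dose in phase II".
- **3.1, raising a dose:** "Intra-patient dose escalation will occur only for patients experiencing Common Toxicity Criteria < grade 2 toxicity on a previous course". The next sentence reads "The intra-patient dose escalation for a patient in lower level dose cohort will be on hold until the highest dose cohort patient completes first cycle", so the setting is escalation across Phase I cohorts. The section then lists dose adjustment among the rules that "as described throughout the protocol will be applied to both Phase I and II".
- **3.1, after a DLT:** "Patients experiencing DLT will be permitted to continue their treatment after a single step dose reduction".
- **3.5, reasons treatment ends:** the list includes "Unacceptable adverse event(s) (DLT").
- **5.1:** grade 3 toxicity leads to a hold and resumption one level lower if indicated; grade 4 takes the patient off protocol therapy.

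The Phase II toxicity rule in 11.1 halts the trial "If ever 5 of the initial cohort of 10 patients experience DLTs, or if ever 8 of the 29 total evaluable phase II patients do".

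**The concern.** Take a patient treated at the RP2D in Phase I, reduced for toxicity, and continuing into Phase II. A site reading 3.1 gives the reduced dose. A site reading 5.2 may go back to the dose at which the toxicity occurred, on the physician's judgment alone. Neither section refers to the other. Before that question even arises, 3.1 and 3.5 disagree on whether a patient with a DLT stays on treatment at all.

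At stake is consistent exposure in patients who have already shown toxicity at the RP2D, and the interpretation of their Phase II safety and response data. These depend on which section is followed.

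**Working it through.** **1. The passages side by side**

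| Patient | One passage | Other passage | Result |
|---|---|---|---|
| Reduced from RP2D in Phase I, continues in Phase II | 3.1: reduced dose in Phase II | 5.2: may return to RP2D at discretion | Direct conflict, no stated precedence |
| Enrolled in Phase II, later reduced | 3.1: increase only after toxicity below grade 2 on a previous course, in Phase I cohort text | 5.2: may return to RP2D at discretion | Unclear, because 3.1 extends dose adjustment to both phases |
| Any patient with a DLT | 3.1: may continue one step lower | 3.5: DLT among the reasons treatment ends | Conflict |

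Section 5.1 decides by grade rather than by DLT status. Grade 4 leaves therapy, so re-exposure mainly concerns grade 3 events.

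**2. Size of the group in direct conflict**

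Under the 3.1 action chart, a level declared MTD has 0 DLTs in 1 patient or 1 in 3 (top level only), or at most 2 in 6. So at most 2 patients treated at the MTD have a DLT during escalation. The number is somewhat larger if reductions after cycle 1 count; the documents give no figure for those. If the RP2D is 100 mg/day, 5.2 allows no reduction and the number is 0.

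**3. Size of the dose difference for such a patient**

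Inputs from 5.2: a 50% quinacrine step; capecitabine 1000 to 750 mg/m².

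- RP2D 400 mg/day: 400 × 0.5 = 200, and 400/200 = 2-fold.
- RP2D 200 mg/day: 200 × 0.5 = 100, and 200/100 = 2-fold.
- Capecitabine, if also reduced: 1000/750 = 1.33, that is 33% higher.

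**4. The halt rule in 11.1**

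With one DLT indicator per patient,

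P(halt) = P(X₁₀ ≥ 5) + Σ (x = 0 to 4) P(X₁₀ = x) · P(X₁₉ ≥ 8 − x).

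- p = 1/3: 0.2131 + (0.0048 + 0.0396 + 0.1264 + 0.2112 + 0.2097) = 0.8050. The plan states 80.5%.
- p = 0.15: 0.0099 + (0.0008 + 0.0057 + 0.0148 + 0.0188 + 0.0127) = 0.0626 (from unrounded terms). The plan states at most 6.3%.

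Both figures reproduce. The rule counts patients who *ever* have a DLT, so a first DLT after re-escalation counts. Only a repeat DLT in a patient already counted adds nothing. Reconciling the dose passages does not change either figure.

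**5. How many Phase II patients could have a DLT**

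The product 29 × 0.333 = 9.7 ignores the halt. Applying the rule patient by patient at p = 1/3 gives an expected 7.0 and a maximum of 8 patients with a DLT before halt or completion.

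**The case against.** The strongest reply is that 3.1 and 5.2 can be read in sequence: 3.1 fixes the dose with which a Phase I patient enters Phase II, and 5.2 governs later changes. That reading is possible, but nothing in either section states it, and 3.1 puts no time limit on the reduced dose. Discretion capped at the RP2D is also a legitimate design choice; the difficulty is only that another section says something else.

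Other parts of the reply stand, and they rule out several stronger readings that a reader might infer.

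- *That 3.1 keeps all reduced patients at the reduced dose.* Its sentence covers only those treated at the RP2D in Phase I.
- *That the below-grade-2 condition plainly contradicts 5.2.* It sits among Phase I cohort rules, whereas 5.2 is limited to Phase II and to returning to the RP2D. Even if the condition applies, it looks at a previous course, so a patient reduced for grade 3 who then has a course below grade 2 could meet it.
- *That toxicity on re-exposure escapes monitoring.* First DLTs count whenever they occur, and missing repeats is inherent in a per-patient rule. All AEs are recorded with grade, attribution and action taken (6.2.1), SAEs are reviewed in real time (12.1), and the DSMB may review toxicity at least every 3 months (12.2).
- *That about 10 of 29 patients are affected.* The halt makes that count impossible. Moreover, grade 4 patients leave therapy, and reduction after grade 3 is only if indicated. Most of these patients are also Phase II enrollees, to whom the direct conflict does not apply.

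**Conclusion.** The concern holds in a limited form. There is one direct conflict (3.1 against 5.2, for Phase I patients reduced from the RP2D), one unresolved question of scope (whether the 3.1 toxicity condition reaches Phase II enrollees), and one related conflict that comes first logically (3.1 against 3.5, on continuing after a DLT).

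The direct conflict affects few patients: at most 2 of 6 with a DLT at a declared MTD, somewhat more if later reductions count, and none at an RP2D of 100 mg/day. For each of them the quinacrine dose differs 2-fold between readings. This assumes that such patients continue into Phase II, as the 3.1 sentence implies. The documents do not say whether they belong to the 29 evaluable patients or whether their Phase I DLT counts there.

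The documents do not support concluding that the Phase II toxicity rule is miscalculated or fails to register re-exposure in general.

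**What to change.** Reconcile 3.1, 3.5, 5.1 and 5.2 so that one rule states:

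1. whether a patient with a DLT continues treatment, and how that fits with the grade 4 provision in 5.1;
2. whether a reduced patient may be re-escalated and, if so, under what condition;
3. which patients the rule covers, naming Phase I carry-overs and Phase II enrollees separately.

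The other sections should then refer to that rule. The clinical content is for the sponsor to decide; this review proposes none.

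The cost is a short text amendment. Sample size and the operating characteristics in 11.1 stay as they are. If the sponsor settles on a stricter rule, physicians lose some discretion. A separate table of DLTs after re-escalation would make repeat events easier to see, because 11.5 tabulates AEs only by type and grade, but it is optional.
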